9.1.5.2. On-Study MRI

Throughout this study, ¹⁸F-fluciclovine PET will be read with standard MRI for anatomical reference. Therefore, all subjects will receive an on-study, study-specific brain MRI scan at Visit 2, ideally on the same day as the PET scan or ≤ 3 days after the PET scan. The on-study MRI will consist of MRI sequences per the minimum standard consensus recommendations

for a standardized brain tumor imaging protocol for clinical trials in brain metastases (BTIP-BM) ([Kaufmann, 2020](#)).

These will include:

- T₁-weighted MRI without and with contrast enhancement,
- FLAIR and/or T₂-weighted MRI, and
- Diffusion-weighted imaging.

On-study MRI brain scans will be uploaded to the central imaging core laboratory by the site investigator/site staff. In addition to reviewing the ¹⁸F-fluciclovine PET scan to identify potential additional PET lesions, on the Visit 2 MRI, the site investigator will confirm the sites of the reference and other equivocal lesions initially defined on the SoC MRI. Full details on the imaging protocol are provided in the Imaging Acquisition Standards. If available, scans acquired on a PET/MRI are allowed.

A final on-study MRI will be performed at Visit 5 (Month 6) only for any surviving subject whose reference or other equivocal lesion(s) remain equivocal at site level, unless an SoC MRI was performed within the preceding 3 weeks.

9.1.6. Vital Signs

Vital signs, including body temperature, blood pressure, pulse and respirations, will be collected at Visit 2 (IMP injection + PET) after resting for at least 5 minutes before IMP injection and after resting for at least 5 minutes following PET scan. The vital signs should be collected between 5 to 60 minutes before and after the PET scan.

9.1.7. SoC Biopsy/Neurosurgical Intervention

Biopsy/resection of the reference / other equivocal lesions is to take place as planned for SoC. Neurosurgical intervention procedures include craniotomy and laser interstitial thermal therapy (LITT) where peri-procedural biopsy is performed. Biopsy/surgical resection of any additional PET lesions may also be performed if clinically applicable. Where a craniotomy is planned, en bloc resection is to be performed where possible. Where en bloc resection is not possible, the surgeon should try and send as much of the sample as possible to enable optimal histopathology assessment. Care should be taken to follow the Sample Handling Laboratory Manual to label all samples sent to the site pathology laboratory, and to reflect the locations sampled and lesion identifiers assigned by the imaging core lab study imaging platform.

The site pathology laboratory will perform histopathology analysis on lesion samples per SoC and will send a representative set of specimens to the central laboratory for analysis. Refer to the Sample Handling Laboratory Manual.

9.1.8. Clinical Follow-Up / Data Abstraction

Clinical follow-up will be performed as SoC per local practice and is anticipated to vary between subjects. For study purposes, clinical data accrued during the period of clinical follow-up, pertaining to the ongoing assessment, eventual confirmation of diagnosis, and treatment of the lesions, will be collected. The data will comprise of brain imaging scans, treatment regimens, histopathological reports and mortality status, see [Table 1](#). Treatment regimens will pertain to treatments and therapies for the brain lesion(s) and primary tumor. These will include and are not limited to systemic treatments such as chemotherapy, immunotherapy and corticosteroids; and localized therapies such as radiotherapy, LITT and

craniotomy, see [Section 9.1.1](#). The period of data accrual will be up to 6 months following ¹⁸F-fluciclovine PET, or death, whichever comes first.

At this visit, an assessment will be performed to evaluate if the patient had experienced neurological deterioration potentially related to progression of brain metastases over the study period. This assessment will be performed by a site investigator who is a board-certified neuro-oncologist, radiation oncologist, medical oncologist or neurosurgeon. As with the other items at this Visit, this assessment will be based on an investigator review of the subject medical record and will take place in the physical absence of the subject.

Based on a review of the subject medical record at the Month 6 Follow-Up visit, the investigator will ascertain if the patient had demonstrated neurological deterioration over the 6-month period. This must be evidenced by one of the following as assessed by the investigator:

1. Notable clinical deterioration corresponding to a significant decline in Karnofsky Performance Status:
 - a. baseline 90/100 decreasing to \leq 70, or
 - b. baseline \leq 80 decrease by \geq 20, or
 - c. any baseline decreasing to \leq 50
2. New or persistent/worsening focal neurological deficit with neuro-anatomical correlation to the site of the reference lesion

If one of the criteria are met, the investigator must also confirm that this impairment:

- Lasted for at least 7 days, and
- Was not attributable to co-morbid events, treatment-related toxicity, changes in corticosteroid dose or progression of systemic disease, and
- Was not altered by therapies for radiation necrosis

If none of the criteria are met (i.e., assessed as no neurological deterioration potentially related to brain metastases), the date of the most recent clinical record to the time of assessment (e.g., a clinical record at 4 weeks prior to Visit 5), which supports the investigator's assessment, should be recorded.

Results of this assessment of neurological deterioration will be used to support diagnostic evaluation at Month 6.

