7.4.5 Statistical/Analytical Issues

7.4.5.1 Handling of Dropouts or Missing Data

Data imputation on missing or indeterminate SoR from the Central Truth Panel on the reference lesion (i.e. subject level only) will be performed according to the following chart:

If the SoR determined by the CTP is not positive/negative then the SoR will be determined using the following rules:

1. If the subject has neurological deterioration at any time during the 6-months follow-up, the SoR will be assigned to positive.
2. If the subject is confirmed not to have neurological deterioration on or after day 141 (6 months with a 4-week time window, i.e. day 169 with a 28-day time window), even if the subject dies after day 141, the SoR will be assigned to negative.
3. Otherwise the SoR will remain as indeterminate.

All subject-level analysis involving SoR will be presented twice, by imputing the remaining indeterminate results as follows:

1. Main analysis of primary and secondary endpoints on subject level diagnostic performance – for each PET reader, the worst case according to that reader (i.e. the opposite finding to the individual PET reader finding) will be imputed
2. Sensitivity analysis 1 of primary and secondary endpoints on subject level diagnostic performance - for each PET reader, the worst case according to the majority of PET readers (i.e. the opposite finding to the PET finding of at least 2/3 PET readers)

To check the validity of the results based on the site's determination of the reference equivocal lesions, these lesions will be measured and confirmed by the central neuroradiologist. A sensitivity analysis on the main endpoint of subject level PPA and NPA, using only subjects with central neuroradiologist confirmation of the reference equivocal lesions, will be performed if there is discrepancy between the site confirmation of reference equivocal lesions vs the central neuroradiologist confirmation.

For lesion level analysis, none of the lesions will be imputed if the SoR designation from the CTP is missing or indeterminate. Lesion-level analysis will only include lesions with SoR designation of positive or negative by the CTP.

7.4.5.2 *Interim Analyses and Data Monitoring*

Not applicable.

7.4.5.3 *Multicenter Studies*

This is a multicenter study, with approximately 18 sites expected to participate. Data collected from all study sites will be pooled for data analysis.

7.4.5.4 *Multiple Comparisons/Multiplicity*

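### Protocol 9.1.8 accepts a persistent focal deficit as deterioration with no pre-PET baseline, so an unchanged old deficit can set the fallback standard of reference to positive

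*Protocol*

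**What the plan says.** At Month 6 a site investigator reviews the medical record, without the subject present, and judges neurological deterioration (Protocol 9.1.8). The question is put as a change over time: "the investigator will ascertain if the patient had demonstrated neurological deterioration over the 6-month period". The section continues, "This must be evidenced by one of the following as assessed by the investigator", so either of two criteria is enough.

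- Criterion 1 is "Notable clinical deterioration corresponding to a significant decline in Karnofsky Performance Status", with three thresholds, each expressed as a fall from baseline.
- Criterion 2 is "New or persistent/worsening focal neurological deficit with neuro-anatomical correlation to the site of the reference lesion". It names no baseline.

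If either is met, the investigator must also confirm three things about the impairment. The first is a minimum duration of one week. The second is about attribution: "Was not attributable to co-morbid events, treatment-related toxicity, changes in corticosteroid dose or progression of systemic disease, and". The third is that treatment of radiation necrosis did not change it.

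SAP 7.4.5.1 uses this assessment only when the CTP has not called the reference lesion positive or negative. Rule 1 reads: "If the subject has neurological deterioration at any time during the 6-months follow-up, the SoR will be assigned to positive". Rule 2 assigns negative if absence of deterioration is confirmed on or after day 141. Rule 3 leaves the subject indeterminate, and the main analysis then imputes the opposite of each reader's finding. SAP 7.4.3 applies these imputations to the primary endpoint.

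**The concern.** A persistent deficit, in the ordinary sense of the word, is one that has not changed. The subjects have irradiated brain metastases, and some may carry a focal deficit from the original tumor into the study. If that deficit is the same at Month 6, criterion 2 can be read as met, although nothing has deteriorated since the PET.

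What is at stake is the truth label in the primary analysis. A subject with treatment-related change and an old fixed deficit could be labelled recurrent. A rule 1 label is the same for all three readers and counts as determined. It therefore stays the same in both presentations of the indeterminate-case imputation in SAP 7.4.5.1, and those presentations would not reveal it. Two qualified investigators could also follow the same page, reach opposite answers for the same subject, and both be able to defend them.

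**Working it through.** **Step 1. Test an unchanged deficit against the text.** Take weakness caused by the original metastasis, mapping to the reference lesion, present before the PET and the same at Month 6.

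| Condition in Protocol 9.1.8 | Met? |
|---|---|
| Deterioration shown over the 6-month period | No, on its plain meaning |
| Criterion 2: new | No |
| Criterion 2: persistent/worsening | Yes if the slash means 'or'; no if both are required |
| Correlates with the reference lesion site | Yes |
| At least 7 days | Yes |
| Not due to co-morbidity, treatment toxicity, steroid change or systemic progression | Yes for a tumor-caused deficit; arguable for a post-surgical one |
| Not altered by radiation necrosis therapy | Yes |

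No confirmation asks when the deficit began. The schedule of procedures lists no baseline neurological examination. The question and criterion 2 therefore give different answers, and the text does not say which governs.

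**Step 2. Follow both readings through SAP 7.4.5.1** (CTP result missing or indeterminate, lesion truly not recurrent).

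| PET read | Deficit counts (rule 1) | Does not count, rule 2 applies | Does not count, rule 3 and worst case |
|---|---|---|---|
| Negative | False negative | True negative | False negative |
| Positive | True positive | False positive | False positive |

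**Step 3. Reproduce the plan's figure.** Inputs from Protocol 15.1: 130 evaluable, prevalence 0.5 (so 65 per class), goal 50%, assumed 70%, one-sided 0.025. The smallest passing count is 41/65: P(X ≥ 41 | n = 65, p = 0.5) = 0.0232. Power is P(X ≥ 41 | n = 65, p = 0.7) = 0.910, which matches the stated 90% for each measure separately. For both measures in one reader, with a fixed 65/65 split, it is 0.910² = 0.828.

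**Step 4. Fixed-count illustration.** Start at 46/65 for both measures (70.8%, exact lower limit 58.2%). Relabel k non-recurrent subjects as positive, where rule 2 would have made them negative; k is assumed. If all k are PET-negative, PPA = 46/(65+k) and NPA = (46−k)/(65−k).

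| k | PPA (lower limit) | NPA |
|---|---|---|
| 3 | 46/68 = 67.6% (55.2%) | 43/62 = 69.4% |
| 5 | 46/70 = 65.7% (53.4%) | 41/60 = 68.3% |
| 9 | 46/74 = 62.2% (50.1%) | 37/56 = 66.1% |
| 10 | 46/75 = 61.3% (49.4%) | 36/55 = 65.5% |

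PPA first fails at k = 10. If instead all k are PET-positive, PPA = (46+k)/(65+k) and NPA = 46/(65−k). For k = 5 these rise to 51/70 = 72.9% and 46/60 = 76.7%.

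**Step 5. At the threshold.** 41/65 passes (lower limit 50.2%). One more PET-negative subject labelled positive gives 41/66, which fails (49.3%, one-sided p = 0.032). In the other direction, 40/65 on both measures fails. Two PET-positive relabelled subjects give PPA 42/67 and NPA 40/63; the smallest passing counts at those sizes are 42 and 40, so both now pass.

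**Step 6. Power illustration.** True PPA = NPA = 70%, k truly negative subjects moved to positive, each with a 30% chance of a positive read. Expected PPA = (65×0.7 + k×0.3)/(65+k).

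| k | Expected PPA | PPA power | NPA power | Joint, one reader |
|---|---|---|---|---|
| 0 | 70.0% | 0.910 | 0.910 | 0.828 |
| 1 | 69.4% | 0.875 | 0.879 | 0.769 |
| 5 | 67.1% | 0.820 | 0.838 | 0.687 |
| 10 | 64.7% | 0.696 | 0.813 | 0.566 |

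Exact tests move in steps as n changes, so only the trend should be read from this table.

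**The case against.** The strongest reply is that the section's question governs. The criteria are evidence of deterioration over the 6 months, judged by a board-certified specialist, and rule 1 itself asks for deterioration during follow-up. An unchanged deficit is neither, and 'persistent/worsening' may be a single joint term. This stands to the extent that a reader who infers that every unchanged deficit counts as deterioration goes beyond the text. It does not remove the conflict, because criterion 2 is offered as sufficient evidence and criterion 1 shows that a change from baseline was written out where it was wanted.

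A reader might also infer that a fixed deficit sets the primary label directly. It does not. Rule 1 is a fallback and never overrides a CTP positive or negative. The Month 6 study MRI for lesions still equivocal adds evidence for the panel, which should limit the number reaching rule 1.

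Three further points stand. A post-surgical deficit may fall under the toxicity exclusion, so the tumor-caused deficit is the sound example. Where rule 2 cannot be applied, a PET-negative subject becomes a false negative anyway under the worst-case imputation, so the wording changes nothing there; for a PET-positive subject it still changes false positive to true positive. And no frequency of fixed deficits is given, so it cannot be claimed that they are common.

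The sensitivity analyses in SAP 7.4.4.6 rest on CTP determinations and give a partial check. They cover subsets and are not the success criterion.

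**Conclusion.** The concern holds as an unresolved conflict between criterion 2, its own governing question and the Karnofsky criterion. In CTP-missing or CTP-indeterminate subjects it can turn the label from negative to positive in the primary PPA and NPA, against or in favor of the product depending on the read. The documents do not establish that an unchanged deficit must count, nor that the trial result would change. In the illustration from 46/65, three or five PET-negative relabelled subjects leave both measures above the goal, and PPA fails only at ten. Near the threshold one or two subjects are enough to change the outcome. These figures assume a 65/65 split, an assumed k, and subjects who would otherwise have been negative under rule 2. The point merits correction because it touches the primary endpoint's truth label and is cheap to remove, not because a large effect has been shown.

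**What to change.** For the purpose of the endpoint definition, reword criterion 2 in Protocol 9.1.8 so that it requires a new focal deficit, or worsening of an existing one, relative to the last clinical record before ¹⁸F-fluciclovine injection, keeping the correlation with the reference lesion site. If 'persistent' was meant as duration, delete it, since the 7-day condition already covers that. Add to SAP 7.4.5.1 that a deficit present before the PET and unchanged since does not trigger rule 1.

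The cost is one sentence in the protocol, one in the eCRF guidance and one in the SAP. The assessment is already a review of the medical record, so no visit or test is added.

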7.3.3 Demographic and Other Baseline Characteristics

Demographic variables including age, sex, ethnicity and race will be summarized for the FAS and SAF. Age will be as recorded on the eCRF and will not be re-calculated.

Age will be summarized using descriptive statistics, and age group (<65 years old, \geq 65 years old). Sex, ethnicity, and race will be summarized with the number and percentage of subjects in each parameter category.

Baseline characteristics include height, weight, body mass index (BMI), Eastern cooperative oncology group (ECOG) performance status, medical history, and prior treatment history. BMI will be calculated as: weight (kg) / [height (cm) / 100]². Height, weight, BMI and ECOG will be summarized for the FAS and SAF; prior treatment history and medical history will be summarized for the FAS only. Height, weight, and BMI at baseline will be summarized using descriptive statistics. ECOG performance status will be summarized with the number and percentage of subjects with each score (0 to 4).

The number of subjects with confirmed equivocal reference lesions by central neuroradiologist will be summarized.

The prevalence data (% positive reference lesions according to SoR) will be summarized.

Primary tumor origin and the corresponding details such as disease staging and molecular profiles, where applicable, will be summarized, along with the extra-cranial (systemic) disease status and time since first known date of diagnosis of brain metastasis(es).

Primary tumor origin will be categorized as Lung Cancer (non-small cell lung cancer [NSCLC] + small cell lung cancer [SCLC]), NSCLC, SCLC, Breast Cancer, Melanoma, and Other (colorectal, pancreatic, kidney, testes, cervix, ovary, head & neck, sarcoma, other). Time (months) since first known date of diagnosis will be calculated as (screening date – first known date of diagnosis of brain metastasis(es))/30.4375. If the date of diagnosis is a partial date and day is not available, then day will be imputed as the 1st of

the month for the purpose of the calculation. If day and month are both not available then the 1st January will be imputed.

Prior cancer treatments for primary tumor will be summarized with the number and percentage of subjects in each of the following categories:

- Surgery
- Lymph nodes dissection
- Radiotherapy
- Other ablative techniques
- Drug therapy

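### When the truth panel cannot call the reference lesion, a Karnofsky decline caused by another brain metastasis can set that lesion's SoR to positive

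*Protocol*

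**What the plan says.** The primary endpoint concerns one lesion per subject. Under SAP 6.1 and 7.4.3, subject-level NPA and PPA compare each blinded reader with the SoR of the reference lesion, and that SoR is normally the Central Truth Panel (CTP) diagnosis.

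SAP 7.4.5.1 covers reference lesions for which the panel result is missing or indeterminate. Its first rule is: "If the subject has neurological deterioration at any time during the 6-months follow-up, the SoR will be assigned to positive". The second assigns negative if absence of deterioration is confirmed on or after day 141. Anything left over is indeterminate, and the main analysis then imputes the opposite of each reader's own finding.

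Deterioration is defined in Protocol 9.1.8, where the site assesses "neurological deterioration potentially related to progression of brain metastases over the study period". On the evidence needed, the section says: "This must be evidenced by one of the following as assessed by the investigator". The two criteria are:

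- "Notable clinical deterioration corresponding to a significant decline in Karnofsky Performance Status", with numerical thresholds;
- "New or persistent/worsening focal neurological deficit with neuro-anatomical correlation to the site of the reference lesion".

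If either is met, the investigator must also confirm a duration of at least 7 days, no change with therapies for radiation necrosis, and this attribution condition: "Was not attributable to co-morbid events, treatment-related toxicity, changes in corticosteroid dose or progression of systemic disease, and".

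**The concern.** The focal-deficit criterion is tied to the reference lesion. The Karnofsky criterion is tied to no lesion, and the attribution list does not repair this. It removes progression of systemic disease, and SAP 7.3.3 treats systemic as extra-cranial ("extra-cranial (systemic) disease status"). Progression of a different brain lesion therefore passes the check.

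Such lesions are expected: the design defines other equivocal lesions and additional PET lesions and has the panel diagnose each one separately. Suppose the reference lesion is radiation necrosis that the panel could not resolve, and a metastasis elsewhere takes Karnofsky from 90 to 70 for more than a week. Every written condition is met, and rule 1 scores the reference lesion as recurrent.

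At stake is the truth label on the primary endpoint. A false-positive read would be credited as a true positive, and a correct negative read would count as a false negative.

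**Working it through.** **Tracing the text**

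1. Entry: the panel result on the reference lesion is missing or indeterminate (SAP 7.4.5.1).
2. Deterioration: the Karnofsky criterion alone suffices and names no lesion (Protocol 9.1.8).
3. Attribution: co-morbid events, treatment toxicity, steroid changes and systemic progression are excluded. Other intracranial progression is not. The 7-day and radiation-necrosis checks do not exclude it either.
4. Assignment: rule 1 gives SoR positive with no further attribution step.

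**Size, by illustration**

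No figure in the plan bears on this point, so there is none to reproduce. The inputs are 130 evaluable subjects and prevalence 0.5, hence 65 positive and 65 negative, with PPA and NPA of 70% (Protocol 15.1, SAP 7.6). The number k of truly negative subjects relabelled positive by rule 1 is an assumption; I take 2, 4 and 6. Readers call 30% of them positive.

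- As written: PPA = (45.5 + 0.3k)/(65 + k); NPA = (45.5 − 0.7k)/(65 − k).
- Left indeterminate with worst-case imputation: the 0.3k positive reads become false positives and the 0.7k negative reads become false negatives. So PPA = 45.5/(65 + 0.7k); NPA = (45.5 − 0.7k)/(65 − 0.7k).

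| k | PPA as written | NPA as written | PPA worst case | NPA worst case |
|---|---|---|---|---|
| 2 | 46.1/67 = 68.8% | 44.1/63 = 70.0% | 45.5/66.4 = 68.5% | 44.1/63.6 = 69.3% |
| 4 | 46.7/69 = 67.7% | 42.7/61 = 70.0% | 45.5/67.8 = 67.1% | 42.7/62.2 = 68.6% |
| 6 | 47.3/71 = 66.6% | 41.3/59 = 70.0% | 45.5/69.2 = 65.8% | 41.3/60.8 = 67.9% |

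**Direction**

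Let f be the share of the k subjects read as positive. As written, PPA = (45.5 + fk)/(65 + k). This exceeds 70% when 45.5 + fk > 45.5 + 0.7k, that is, when f > 0.7. At the extreme f = 1:

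- k = 5: as written, PPA = 50.5/70 = 72.1% and NPA = 42/60 = 70.0%. Under worst case, 45.5/65 = 70.0% and 42/65 = 64.6%.
- k = 10: as written, PPA = 55.5/75 = 74.0% and NPA = 38.5/55 = 70.0%. Under worst case, 70.0% and 38.5/65 = 59.2%.

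For a PET-negative read the two treatments agree: both give a false negative. They differ only for a PET-positive read, which rule 1 counts as a true positive and worst-case imputation as a false positive. For these subjects, then, rule 1 is never less favourable to the reader than the SAP's own conservative fallback.

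**The case against.** The strongest reply is that the gap is narrow.

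- **Reach.** A reader might infer that another metastasis can overturn the truth label in any subject. It cannot: rule 1 applies only where the panel has made no positive or negative call. The panel works lesion by lesion on 6 months of data, and a reference lesion still equivocal at the site at Month 6 gets a final MRI unless a recent one exists. The example also needs the panel to fail on that lesion. This stands and limits the point.
- **Treatment complications.** A reader might infer that complications of treating other brain lesions slip through too. The exclusions for treatment-related toxicity and steroid changes name no lesion, so they largely cover this. The gap is progression.
- **Co-morbid event.** An investigator might file another metastasis under this heading. The text does not say so, and progression of brain metastases is what the assessment is meant to find.
- **Other checks.** Lesion-level analyses use only panel calls, and the two analyses in SAP 7.4.4.6 base SoR on panel determinations. These help, but only partly: the former answer a different question and the latter use restricted subsets. The sensitivity analysis in SAP 7.4.5.1 varies only what is still indeterminate after rule 1, so it does not test rule 1.
- **Unseen material.** The panel charter and the SAP chart are not available here. The written rules contain no attribution step.
- **The remedy.** Leaving these subjects indeterminate does not rescue a correct PET-negative read, and on average both estimates move further from 70%. This is correct. The gain is that PET-positive reads are no longer wrongly credited.

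**Conclusion.** The point holds for panel-unresolved reference lesions. In that group, following the plan as written can label the reference lesion recurrent because of a different brain lesion.

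The size cannot be determined from the documents. Under the assumptions above (65/65, 70%/70%, k of 2 to 6, 30% read positive), PPA falls by 1.2 to 3.4 points and NPA does not change on average.

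A reader might infer a systematic bias toward trial success. The documents do not support that: with average reads the error lowers PPA, and it raises PPA only if more than 70% of the mislabelled subjects are PET-positive. Nothing in the plan shows which case applies. This is a definitional gap that should be closed before database lock, not evidence that the primary analysis is invalid.

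**What to change.** 1. Protocol 9.1.8, second confirmatory bullet: after the reference to systemic disease, add *or progression of brain lesions other than the reference lesion*.
2. SAP 7.4.5.1: state that a deterioration attributed to another brain lesion does not trigger rule 1. State also that it must not be recorded as absence of deterioration and so turned negative by rule 2. The subject stays indeterminate and receives the planned worst-case imputation. Without this sentence, the protocol clause alone could replace one unverified label with another.
3. Report how many reference-lesion SoRs were set by rule 1.

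The cost is one clause in the protocol and eCRF, a short addition to the SAP, and one count in the report. The price is that a few more subjects are imputed worst-case, so the estimates become slightly less favourable: about 68.5%/69.3% (PPA/NPA) at k = 2 and 65.8%/67.9% at k = 6, against 68.8%/70.0% and 66.6%/70.0% as written. The change concerns truth assignment only, not patient management.
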